7.3 Return and disposal of unused investigational product

After administration of CARTISTEM[®], the amount of any empty containers or remaining drug shall be documented on a designated form and returned to the Contract Manufacturing Organization (CMO).

The CMO will then verify the amount of any remaining drugs indicated on the form and store them frozen for one year after its receipt of the returned investigational product. Thereafter, the CMO will dispose the returned drug per its operating procedure.

CARTISTEM®

page 31 of 137

CONFIDENTIAL: These all contents herein are the sole property of MEDIPOST Co., Ltd. Any reproduction or distribution of this document without the written consent of MEDIPOST Co., Ltd is prohibited. Copyright © 2017 MEDIPOST Co., Ltd.

8 Study Method

8.1 Overview of the Study Design

This study is a phase I/IIa open-label clinical trial with the objective of assessing the safety and exploratory efficacy of a single administration of CARTISTEM[®], an allogeneic-unrelated umbilical cord blood-derived mesenchymal stem cell product, in patients with articular cartilage defects.

CARTISTEM®

page 32 of 137

CONFIDENTIAL: These all contents herein are the sole property of MEDIPOST Co., Ltd. Any reproduction or distribution of this document without the written consent of MEDIPOST Co., Ltd is prohibited. Copyright © 2017 MEDIPOST Co., Ltd.

8.2 Study Flow Chart

	Screening (Week – 6~Week 0)	Baseline (Day -2) (±2d)	Treatment (Day 0)	Week 2 (±5d)	Week 4 (±5d)	Week 8 (±5d)	Week 12 (±7d)	Week 24 (±14d)	Month 12 (±30d)	Month 24 (±30d)
Visits	1	2	3	4	5	6	7	8	9	10
Informed Consent	•									
Physical Examination ¹⁾	•								٠	
Medical History, Medication History ¹⁾	•									
Inclusion/Exclusion Criteria	•									
Pregnancy Test (Serum HCG)	•	•								
Vital Signs/Temperature										
Laboratory Tests ²⁾	•3)			● ⁴⁾						
Immunogenicity tests (T cell subset)	● ⁵⁾							•		
X-ray of the Joint										
MRI (T2 mapping)	● ⁶⁾							•	●7)	●7)
Administration of the Investigational Product ⁸⁾			•							
IKDC Score ⁹⁾										

CARTISTEM®

page 33 of 137

CONFIDENTIAL: These all contents herein are the sole property of MEDIPOST Co., Ltd. Any reproduction or distribution of this document without the written consent of MEDIPOST Co., Ltd is prohibited. Copyright © 2017 MEDIPOST Co., Ltd.

	Screening (Week – 6~Week 0)	Baseline (Day -2) (±2d)	Treatment (Day 0)	Week 2 (±5d)	Week 4 (±5d)	Week 8 (±5d)	Week 12 (±7d)	Week 24 (±14d)	Month 12 (±30d)	Month 24 (±30d)
Lysholm Score										
KOOS Score										
100-mm VAS Evaluation ¹⁰⁾		•		●11)	•	•	•	•	•	•
Check for Concomitant Medications		•		•	•	•	•	•	•	•
Check for Adverse Events/Toxicity						•	•	•		•

- 1) Name, gender, date of birth, address, height, body weight, medical history, concomitant medications
- 2) Hematology: Hematocrit, Hemoglobin, MCV, MCH, MCHC, RBC, WBC, Platelet, Differential count (Neutro, Eosino, Baso, Lympho, Mono)

Blood Chemistry: GOT (AST), GPT (ALT), Alkaline Phosphatase, Glucose, Urea (BUN), Creatinine, Direct bilirubin, CK, LDH, Uric acid, Albumin, and Total Protein

Blood Coagulation: PT, aPTT

Electrolytes: Sodium, Potassium, Chloride

Urinalysis: Color, Specific gravity, pH, Leucocytes, Nitrite, Protein, Glucose, Ketone, Urobilinogen, Bilirubin, RBC, Microscopy

- 3) Lab test at Screening can be used as the pre-treatment baseline.
- 4) Lab Tests for patient at Week 2 can be omitted if the lab tests within the window period for Week 2 (i.e. 9 to 19 days after operation) are available.
- 5) Immunogenicity test at Screening can be used as the pre-treatment baseline.
- 6) MRI (T2 mapping) performed for at Screening may be skipped if MRI (T2 mapping) within the past 6 months is available. MRI (T2 mapping) at Screening can be used as the pre-treatment baseline.
- 7) MRI performed at Week 24 and Months 12 and 24 will also evaluate for tumorigenicity at focal lesion of the knee administration

CARTISTEM®

page 34 of 137

CONFIDENTIAL: These all contents herein are the sole property of MEDIPOST Co., Ltd. Any reproduction or distribution of this document without the written consent of MEDIPOST Co., Ltd is prohibited. Copyright © 2014 MEDIPOST Co., Ltd.

site.

- 8) Administration of the Investigational Product: 500 μ L/cm² of defect size
- 9) From baseline to Week 24, only subjective knee evaluation form must be filled in.
- 10) Use of NSAIDs must be discontinued for 6 weeks prior to treatment and may be resumed following the treatment. Use of NSAIDs and any other analgesics must be discontinued for 48 hours and 24 hours, respectively, prior to VAS evaluation at Weeks 4, 8, 12, and 24, and Months 12 and 24.
- 11) Patient may be allowed to take analgesics within 24 hours prior to VAS evaluation at Week 2.

The subject must visit the center on the scheduled visitation date ± 5 days for Weeks 2, 4, and 8; ± 7 days for Week 12, ± 14 days for Week 24 after the administration of the investigational product. For the long term follow-up patient assessment, the subject must visit the center on the scheduled visitation date ± 30 days at Months 12 and 24.

CARTISTEM®

page 35 of 137

CONFIDENTIAL: These all contents herein are the sole property of MEDIPOST Co., Ltd. Any reproduction or distribution of this document without the written consent of MEDIPOST Co., Ltd is prohibited. Copyright © 2014 MEDIPOST Co., Ltd.

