The primary objective of the proposed single-center phase I/IIa study is to evaluate the safety of CARTISTEM[®], an allogeneic-unrelated mesenchymal stem cell (hUCB-MSC) suspension mixed with sodium hyaluronate, at doses ranging from 0.5×10^7 to 2.25×10^7 hUCB-MSC in patients with articular cartilage defects that are equal or greater than 2cm².

The secondary objective of the study is to evaluate the efficacy (regeneration of defective cartilage and decrease of pain) of CARTISTEM[®].

CARTISTEM[®] will be administered, as a function of the defect size, at a cell density of 0.25×10^7 cells/cm² (0.5 mL/cm² with 0.5×10^7 hUCB-MSC/mL) directly into the articular cartilage defect by open surgery.

CARTISTEM®

page 18 of 137

CONFIDENTIAL: These all contents herein are the sole property of MEDIPOST Co., Ltd. Any reproduction or distribution of this document without the written consent of MEDIPOST Co., Ltd is prohibited. Copyright © 2017 MEDIPOST Co., Ltd.

A total of 12 patients, initially 6 patients with defect sizes of 2 to 5 cm² (Dosage A) followed by an additional 6 patients with defect sizes of above 5 cm² (Dosage B), will be enrolled sequentially in 2 groups in order to evaluate whether dose-limiting toxicity (DLT) is detected.

Each patient will undergo a 6-week screening period for eligibility and a 12-month follow-up observation period for both the primary (safety) and secondary (efficacy) endpoints of the study. There is an additional long term follow-up observation visit at 24 months. The estimated total duration of the study is approximately 24 months.

Prior to administration of CARTISTEM[®], the defect will undergo debridement, and following appropriate preparation, perforation of the subchondral plate.

CARTISTEM[®] is applied directly onto the entire defect site.

For use at the clinical site, CARTISTEM[®] will be provided as a cell suspension and lyophilized sodium hyaluronate in separate glass vials.

In terms of post-operative rehabilitation, patients will be started on a continuous passive motion (CPM) device on post-operative day 1 and refrain from high-impact activities such as running for 20 to 24 weeks.

6 Study Design

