6.2 Subject Selection Criteria

- 1) Inclusion Criteria
- A. Patients with an intended- to- treat single focal, full-thickness cartilage defect (ICRS [International Cartilage Repair Society] Grade 3 or 4) of the knee as a result of ageing,

CARTISTEM®

page 19 of 137

CONFIDENTIAL: These all contents herein are the sole property of MEDIPOST Co., Ltd. Any reproduction or distribution of this document without the written consent of MEDIPOST Co., Ltd is prohibited. Copyright © 2017 MEDIPOST Co., Ltd.

trauma, or degenerative diseases

- B. Age \geq 18 years old
- C. Size of the articular cartilage lesion is $\ge 2 \text{ cm}^2$
- D. Swelling, tenderness and active range of motion \leq Grade II
- E. Joint pain : 20-mm 60-mm on VAS (Visual Analog Scale) at the time of Screening
- F. Appropriate blood coagulation, kidney and liver function laboratory parameters:
 - ✓ PT(INR) < 1.5, APTT <1.5×control
 - ✓ Creatinine \leq 2.0 mg/dL, Albumin \leq trace in urine dipstick test
 - ✓ Bilirubin \leq 2.0 mg/dL, AST/ALT \leq 100 IU/L
- G. Ligament instability \leq Grade II
- H. Lower extremity alignment within 5 degrees of the neutral weight bearing axis
- I. No meniscal surgery within the past 3 months and more than 5mm of meniscal rim remaining
- J. Ability and willingness to fully participate in the post-operative rehabilitation program
- K. Subject is informed of the investigational nature of this study, voluntarily agrees to participate in the study, and signs an IRB-approved informed consent prior to performing any of the screening procedures
- L. Body Mass Index (BMI) \leq 35 kg/m²
- 2) Exclusion Criteria
- A. Patients that have been treated previously and are asymptomatic
- B. Avascular necrosis / osteonecrosis
- C. Autoimmune or inflammatory joint disease
- D. History of infection within the past 6 weeks
- E. Surgery or radiation therapy within the past 6 weeks
- F. Serious medical co-morbidities which would otherwise contraindicate surgery, as determined by the investigator
- G. Currently pregnant or nursing
- H. Psychotic diseases, epilepsy, or any history of such diseases

CARTISTEM®

page 20 of 137

CONFIDENTIAL: These all contents herein are the sole property of MEDIPOST Co., Ltd. Any reproduction or distribution of this document without the written consent of MEDIPOST Co., Ltd is prohibited. Copyright © 2017 MEDIPOST Co., Ltd.

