8.4.10 MRI Assessment

Structural information will be gained using high-resolution (1.5 or 3 Tesla) magnetic resonance imaging (MRI) at Screening, week 24, month 12, and month 24 in order to evaluate the clinical symptom improvement. The MRI evaluations at week 24, month 12 and month 24 will also evaluate for tumorigenicity at focal lesion.

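### The baseline MRI may be up to 6 months old, at a different field strength from follow-up, and may pre-date a permitted procedure on the study knee

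*Combined protocol and SAP*

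**What the plan says.** All references are to the combined protocol and SAP.

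- **8.2 Study Flow Chart, footnote 6.** The Screening MRI "may be skipped if MRI (T2 mapping) within the past 6 months is available". The footnote adds: "MRI (T2 mapping) at Screening can be used as the pre-treatment baseline".
- **8.4.10 MRI Assessment.** The section calls for "high-resolution (1.5 or 3 Tesla) magnetic resonance imaging (MRI) at Screening, week 24, month 12, and month 24". Screening is the only pre-treatment time point in this list. Section 10.3.1 repeats the choice of field strength and names T2 mapping.
- **6.2 Subject Selection Criteria.** Exclusion E reads "Surgery or radiation therapy within the past 6 weeks". Inclusion I begins "No meniscal surgery within the past 3 months". Exclusion A removes "Patients that have been treated previously and are asymptomatic", so a previously treated patient who still has symptoms remains eligible.
- **Section 5, Purpose of the Study.** "Each patient will undergo a 6-week screening period for eligibility".
- **Synopsis, Statistical Methods.** Each efficacy endpoint is to be tested on its change from baseline. Section 10.3.1 lists MRI among the efficacy variables after the primary IKDC endpoint, and the synopsis overview classes it as secondary.

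**The concern.** A within-patient change is interpretable only if the two scans are comparable and nothing but the study intervention and its aftermath lies between them. Following the plan as written can break both conditions. A patient may have a baseline at one field strength and follow-up at the other. A patient may also have had a knee procedure after the baseline scan and before enrolment.

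MRI is the only structural measure among the efficacy variables, and cartilage regeneration on imaging is part of the secondary objective. Each cohort has 6 patients, so a few non-comparable baselines carry weight in a mean. An unsuitable baseline cannot be replaced after implantation, so the rule has to be set beforehand.

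**Working it through.** The plan gives no sample size, standard deviation or alpha for MRI, so it has no figure to reproduce. The check uses the plan's own time limits, with 1 month = 30.44 days.

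**1. Does the historical scan become the baseline?** Footnote 6 lets it replace the Screening MRI. The flow chart and 8.4.10 schedule no other MRI before treatment. It is therefore the only available comparator.

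**2. How old can it be at implantation?** Footnote 6 does not say from which date the 6 months run. Read as screening:
- 6 × 30.44 = 182.6 days = 26.1 weeks at screening.
- Adding the 6-week screening period: 182.6 + 42 = 224.6 days = 32.1 weeks = 7.4 months.
- A scan done in the screening period is at most 6 weeks old. Ratio: 32.1 / 6 = 5.3.
- Scan to Month 12, with the +30 day window: 7.4 + 12 + 1.0 = 20.4 months.

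If the 6 months run back from treatment instead, the maximum at implantation is 6 months.

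**3. Can a permitted procedure fall after the scan?** With all limits counted back from screening:

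| Procedure | Excluded if more recent than | Oldest permitted scan | Window in which it can follow the scan |
|---|---|---|---|
| Non-meniscal surgery | 6 weeks | 26.1 weeks | 26.1 − 6 = 20.1 weeks |
| Meniscal surgery | 3 months (13.0 weeks) | 26.1 weeks | 26.1 − 13.0 = 13.0 weeks (unrounded) |

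Exclusion E covers surgery in general and makes no exception for the knee. No section asks for a new MRI after such surgery. A scan taken in the screening period could not pre-date permitted surgery on this count.

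**4. Is scanner consistency required?** T2 mapping is fixed: the flow-chart row specifies it, and footnote 6 accepts only a scan that has it. Field strength is open (1.5 or 3 Tesla). No section requires one field strength, or one set of T2 acquisition parameters, across a patient's visits. This applies to every pair of visits, not only to historical baselines.

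**5. What could it do to a mean?** If k of n patients have a mismatch offset d in the same direction, the mean change shifts by d × k/n. For one patient of 6 the shift is d/6; for three of 6 it is d/2. Switches in opposite directions partly or wholly cancel. The documents give neither d nor the standard deviation of change, so the calculation stops here.

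**The case against.** The strongest reply is that little rests on this scan. The primary objective is safety, primary efficacy is IKDC at 12 months, and the dose follows the defect size measured after debridement at surgery (7.2.5). Efficacy is exploratory, without a power calculation. Section 10.3.1 describes a grade of regeneration and the morphology of the repair area, which is largely a post-operative reading. No T2-change score is defined, and analysis of change rests on one general synopsis sentence. Use of a historical scan is optional, and exclusion Q lets the investigator refuse an unsuitable patient. All of this stands, and it limits the weight of the point.

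It does not remove the point. The synopsis sentence covers every efficacy endpoint, and a site following footnote 6 exactly can produce a non-comparable baseline.

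Three stronger readings are tempting and are not supported:
- **The tumorigenicity assessment is compromised.** Footnote 7 and 8.4.10 place it at Week 24 and Months 12 and 24. Neither defines it as a change from baseline.
- **Footnote 6 is why change cannot be attributed to the implant.** The trial has no reference therapy, and every defect is debrided and drilled before implantation. Attribution is limited by design, even with a matched baseline.
- **The bias can be stated as a percentage of T2.** Any such figure needs a platform offset that the documents do not contain.

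Nor does the point depend on a difference between centres. The synopsis gives two centres, while Section 5 describes a single-center study.

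**Conclusion.** The point holds as a weakness in a stated rule. A T2-mapping MRI up to 6 months old at screening, or about 7.4 months at implantation, can be the only baseline. It can differ in field strength or acquisition parameters from the follow-up scans, and it can pre-date a permitted procedure on the study knee. Any change from baseline in the MRI endpoint may partly reflect either.

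The 7.4 months and the 20.1- and 13.0-week windows are maxima that the text allows, not expected exposures. They assume that the limits are counted at screening. How many patients would be affected, and by how much, cannot be derived from the documents. A reader might infer that observed T2 or repair change would be an artefact; the text supports only that part of it could be. Safety, IKDC and dosing do not depend on this scan. The point is a cheap improvement.

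**What to change.** In footnote 6 and 8.4.10:

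1. Require the same field strength and the same T2-mapping acquisition parameters for all MRIs of a patient.
2. Accept a historical MRI as baseline only if it meets that requirement and no procedure on the study knee has occurred since it was taken.
3. Otherwise, perform the Screening MRI already in the schedule.

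This removes scanner mismatch and intervening procedures. It does not by itself shorten the permitted age of a matching scan.

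The cost is protocol wording. A few patients would have the scheduled Screening MRI instead of reusing an existing scan, and each patient's follow-up scans must be booked on a matching scanner. No visit or procedure is added to the schedule.

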Efficacy Evaluation	Primary efficacy outcome parameters will be the postoperative changes in subjective knee function as assessed by IKDC (International Knee Documentation Committee) score at 12 months. For secondary efficacy outcome parameters, patients will answer questionnaires for pain (visual analogue scale, VAS), knee specific outcome instruments (Lysholm knee scoring, and KOOS [Knee injury and Osteoarthritis Outcome Score]). Structural information will be gathered using high-resolution (1.5 or 3 Tesla) magnetic resonance imaging (MRI).

page 7 of 137

CONFIDENTIAL: These all contents herein are the sole property of MEDIPOST Co., Ltd. Any reproduction or distribution of this document without the written consent of MEDIPOST Co., Ltd is prohibited. Copyright © 2017 MEDIPOST Co., Ltd.

Statistical Methods	General: all safety and efficacy endpoints will be presented for each dose cohort as well as for all patients combined. For safety evaluation, statistical homogeneity between dose groups will be performed. For efficacy evaluation, statistical comparison (difference) between dose groups will be performed.
	1) Safety Safety will be demonstrated with 95% confidence intervals. Adverse events, adverse drug reactions, serious adverse events, and drop-out patients due to AE will be presented with frequency and percentage. Homogeneity between dose groups will be analyzed using person's chi-square test or Fisher's exact test. Descriptive statistics including means, medians, SD (standard deviation), minimum and maximum will be used to demonstrate the other safety endpoints.
	2) Efficacy Symptom improvement from the outcome instruments will be demonstrated with means and standard deviations. Efficacy results will also be analyzed for statistical significance using change from baseline at each efficacy endpoint. Statistical difference of continuous variables and categorical variables between dose groups will be compared using t-test and Fisher's exact test, respectively.
Rationale for Study Population and Number of Patients	CARTISTEM [®] is administered to the defective joint cartilage region by open surgery. Due to ethical considerations, it is not possible to conduct this type of procedure in a healthy subject. Therefore, no studies in healthy subjects will be performed.

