8.3 Concomitant Medications and Concomitant Non-drug Therapies

Concomitant treatment with systemic corticosteroids or immunosuppressants is not permitted, but co-administration of any other drugs that have no effect on the efficacy assessment is allowed. If there is a concomitant medication, the name of the drug's active ingredient (name of the product in case of a combination drug), dosage, starting/ending date of administration, and the reasons for administration are to be recorded on the case report form (CRF). Information on any concurrent therapies (ex: physiotherapy) are also required to be documented on the CRF (type, duration, etc.). All concomitant medications and therapies are to be recorded at baseline and during the trial.

The following drugs are not permitted: glucosamine, dietary supplements used as alternative medicine to treat osteoarthritis such as chondroitin sulfate and hyaluronan, systemically administered corticosteroids (Hydrocortisone, Prednisone, Prednisolone, Methylprednisolone, Triamcinolone, Dexamethasone, Paramethasone, Betamethasone, Aldosterone, Fludrocortisone) and immunosuppresant (Prednisone, Vincristine, Azathioprine, γ - globulin, Cyclophosphamide, Chlorambucil, 6-mercaptopurine, Cyclophosphamide + factor XIII, Rh(D) immune globulin, ALG, Actinomycin-D, OKT3, Methotrexate

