8.4.6 IKDC Score

page 38 of 137

CONFIDENTIAL: These all contents herein are the sole property of MEDIPOST Co., Ltd. Any reproduction or distribution of this document without the written consent of MEDIPOST Co., Ltd is prohibited. Copyright © 2017 MEDIPOST Co., Ltd

The subjects will undergo a self-assessment of knee function using IKDC subjective knee evaluation score before and after the drug administration in order to determine the efficacy of the investigational product. The IKDC assessment will be performed at the 4, 8, 12, 24 weeks and 12 and 24 months after the drug treatment in an exploratory fashion but the IKDC score from the 12 month time point will be used as a primary result of the post-operative change.

8.4.7100-mm VAS Evaluation

The subjects will undergo a self-assessment of joint pain using 100 mm VAS before and the 2, 4, 8, 12, 24 weeks and 12 and 24 months after the drug administration for the efficacy evaluation. Use of NSAIDs must be discontinued for 6 weeks prior to treatment and may be resumed following the treatment. Use of NSAIDs and any other analgesics must be discontinued for 48 hours and 24 hours, respectively, prior to VAS evaluation at Weeks 4, 8, 12, and 24, and Months 12 and 24. Patient may be allowed to take analgesics within 24 hours prior to VAS evaluation at Week 2.

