10.3.2 Analysis of Efficacy Endpoints

The descriptive statistics of the categorical variables will be presented with percentage and frequency and that of the continuous variables such as mean, median, standard deviation, and interquartile range. The primary efficacy endpoint will be analyzed using the t-test. As for the secondary efficacy endpoints, differences of the continuous variables and the categorical variables between the two groups will be analyzed using the t-test and Fisher's exact test, respectively.

CONFIDENTIAL: These all contents herein are the sole property of MEDIPOST Co., Ltd. Any reproduction or distribution of this document without the written consent of MEDIPOST Co., Ltd is prohibited. Copyright © 2017 MEDIPOST Co., Ltd

11 Rehabilitation Protocol

All patients must participate in the following standardized rehabilitation program after receiving treatment. Rehabilitation program will vary according to the defect location of each subject.

Stage 1- Proliferative Phase (Week 1 to 6)

Femoral Condyle Defect

	PRIMARY GOALS
	DO NOT OVERLOAD GRAFT
	INCREASE TIBIOFEMORAL AND PATELLOFEMORAL MOBILITY
	RESTORE QUADRICEPS CONTROL
BRACE	• Knee immobilizer with ambulation, until good quads control/SLR (approximately Week 3 to 6)
GAIT	Heel-toe TDWB with crutches
ROM	• Full AROM and gentle AAROM.
	 CPM ≥ 6 to 8 hours daily for 6 weeks. Start at 0-40 degrees, progress range as tolerated.
	• Goal: minimum 90 degrees flexion for the first 2 weeks, 110 degrees for the next 4 weeks (the 6 week time point of post-op)
THEREX	• Quad sets, SLR in knee immobilizer as needed, leg curl/heel slides, hip abduction
	 Stationary bicycle with no resistance once 90 degrees knee flexion obtained (~ 4 weeks).
	 90 degree leg dangle hourly to improve ROM
THERAPY	 Gentle multi-directional patella mobilization starts immediately after surgery. Cryotherapy and compression stockings/TEDS for swelling and pain control. E-stim for VMO/quadriceps muscle re-education/biofeedback encouraged
	early after surgery if needed.
	 Gentle massage/deep friction to hamstring insertions, suprapatellar quadriceps, medial/lateral gutters, and infrapatellar fat pad region at 2-3 weeks post-op.
	 Pool therapy recommended 2-3 weeks post-op to enhance motion.
	• Foot merapy recommended 2-5 weeks post-op to emiance motion.

page 44 of 137

Femoral Condyle Defect

PRIMARY GOALS DO NOT OVERLOAD GRAFT INCREASE TIBIOFEMORAL AND PATELLOFEMORAL MOBILITY RESTORE QUADRICEPS CONTROL

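### The 24-hour stop of non-NSAID analgesics applies to six follow-up VAS visits but not to Baseline, so a medicated baseline can be set against unmedicated follow-up

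*Combined protocol and SAP*

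**What the plan says.** Two analgesic rules are attached to the VAS row of the flow chart (section 8.2, footnote 10) and repeated in section 8.4.7.

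- **Before treatment, NSAIDs only:** "Use of NSAIDs must be discontinued for 6 weeks prior to treatment and may be resumed following the treatment".
- **Before follow-up VAS, all analgesics:** NSAIDs stop for 48 hours and other analgesics for "24 hours, respectively, prior to VAS evaluation at Weeks 4, 8, 12, and 24, and Months 12 and 24".

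Footnote 11 adds an exemption: "Patient may be allowed to take analgesics within 24 hours prior to VAS evaluation at Week 2".

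The VAS row is marked at Baseline (Day -2), and section 8.4.7 confirms a pre-treatment score: "The subjects will undergo a self-assessment of joint pain using 100 mm VAS before and the 2, 4, 8, 12, 24 weeks", continuing to Months 12 and 24. The VAS instructions, printed at the end of Appendix 2, ask the patient to rate knee pain over the preceding 24 hours.

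Section 8.3 has a general clause on other medication: "co-administration of any other drugs that have no effect on the efficacy assessment is allowed". It also says "All concomitant medications and therapies are to be recorded at baseline and during the trial".

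On analysis, the synopsis states: "Efficacy results will also be analyzed for statistical significance using change from baseline at each efficacy endpoint". For secondary endpoints, section 10.3.2 says that "differences of the continuous variables and the categorical variables between the two groups will be analyzed using the t-test" for the continuous ones. There is no reference therapy.

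**The concern.** The protocol treats a 24-hour analgesic stop as a condition for a usable VAS score at six visits, which matches the recall period of the form. It does not set that condition for the one score from which every change is calculated. A patient on a non-NSAID analgesic before Day -2 and off it at follow-up is measured under two different conditions. The recorded baseline is then too low and the improvement too small.

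With no control arm, nothing offsets this in the change from baseline. Pain reduction is named in the secondary objective (section 5), and an understated pain signal could mislead the planning of later trials. Non-NSAID use before Baseline is plausible, because patients enter with 20 to 60 mm of pain and must be off NSAIDs for 6 weeks. The documents do not show that any patient would take such a drug.

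**Working it through.** **Step 1: rules against the VAS schedule.** The flow chart marks eight VAS visits.

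| VAS visit | NSAIDs | Other analgesics |
|---|---|---|
| Baseline (Day -2) | stopped (6 weeks before treatment) | no rule |
| Week 2 | exempt (footnote 11) | exempt (footnote 11) |
| Weeks 4, 8, 12, 24; Months 12, 24 | 48-hour stop | 24-hour stop |

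Baseline is the only marked visit with neither a stop nor an exemption for other analgesics. The prohibited-drug lists (synopsis and section 8.3) and the eligibility criteria (section 6.2) name no analgesic.

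**Step 2: direction.** Let B be a patient's unmedicated baseline score, F the unmedicated follow-up score and d the lowering of the baseline by an analgesic. The recorded improvement is (B - d) - F, against a true B - F, so it is understated by d.

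**Step 3: effect of one patient on the mean.** The plan gives no figure to reproduce here. The inputs are the planned sizes (6 per cohort, 12 in all; section 6.3) and assumed values of d. The shift in mean change is d/n.

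| Assumed d | n = 6 | n = 12 |
|---|---|---|
| 5 mm | 5/6 = 0.83 mm | 5/12 = 0.42 mm |
| 10 mm | 10/6 = 1.67 mm | 10/12 = 0.83 mm |
| 20 mm | 20/6 = 3.33 mm | 20/12 = 1.67 mm |

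With k medicated baselines, each with the same d, multiply by k. With none, the shift is zero.

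**Step 4: Dosage A against Dosage B.** With kA and kB medicated baselines in two cohorts of 6, the between-cohort difference shifts by d × (kA - kB)/6. This is 0 when kA = kB. It is 10 × 1/6 = 1.67 mm when the counts differ by one patient and d = 10 mm.

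**The case against.** The strongest reply is that section 8.3 already covers Baseline. It allows other drugs only if they do not affect the efficacy assessment, and an analgesic inside the recall period of the form would affect it. The wording of footnote 11 can also be read as an exception to a default ban. This shows that the text is open to argument, but it does not settle the matter. Section 8.3 names no analgesic and no time window. Footnotes 10 and 11 presuppose that patients take analgesics and regulate them visit by visit; under a standing ban, the 24-hour rule would be redundant.

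Several limiting points stand:

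- NSAIDs are excluded at Baseline more strictly than at follow-up, so only other analgesics are at issue.
- No trial decision depends on VAS change. Escalation, stopping and the MTD rest on DLT counts, and the DLT pain criterion is an absolute 80 points. The primary efficacy endpoint is the IKDC score at 12 months.
- The bias in change from baseline understates benefit, so it cannot create a false claim of improvement. A bias common to both cohorts cancels in the comparison of A with B.
- Every value of d is an assumption.

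One further point stands conditionally. Dosage A is enrolled before Dosage B. If Dosage A patients have already passed Baseline, a rule added now would place the cohorts under different baseline conditions and could itself introduce a difference between them. The documents do not give enrolment status. The date flag proposed below handles this only in part.

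**Conclusion.** The concern holds. Followed as written, the plan permits a baseline VAS taken under a non-NSAID analgesic to be compared with follow-up scores taken without one, at all six visits that carry the stop. The size cannot be estimated from the documents. Under the assumed 5 to 20 mm, each affected patient moves a cohort mean by 0.8 to 3.3 mm and the overall mean by 0.4 to 1.7 mm.

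These figures assume cohorts of 6, complete data and full adherence to the follow-up stop. The consequence is modest: a conservative bias in an exploratory secondary endpoint of a safety trial. The change is still worth making, because it applies a rule that the protocol already uses elsewhere and costs very little. Confidence is medium, since use of such drugs before Baseline is unknown and section 8.3 leaves some room for a different reading.

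**What to change.** Add Baseline to the visits with the 24-hour stop of other analgesics, in footnote 10 of section 8.2 and in section 8.4.7.

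For any patient already past Baseline, mark in the VAS listing whether a non-NSAID analgesic was in use at that visit, from the concomitant medication record. The CRF holds start and end dates, not the time of the last dose, so the flag is by date and cannot confirm use within 24 hours. If the new rule takes effect between the cohorts, read the comparison of A with B alongside this flag.

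The cost is one visit added to a sentence in two places, and one flag in a listing of about 12 patients. No new visit or data collection is needed. The burden on patients is 24 hours without other analgesics before the Baseline visit, at a time when they are already off NSAIDs. The same 24-hour stop is already required at six later visits.
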